### **2.) Chart Extraction:**

The medication list from the patient's EMR will be provided by the patient. This printed-out medication list will be used to a) obtain name, medical record number (MRN) and date of birth (DOB) to establish identity and be validated by the patient and b) to confirm with the patient medications to be entered into the app. If there are any discrepancies between what the patient says they are taking and what is listed on their medication list, the PI will consult with the patient directly. All identifying information on the printed-out copy of the medication list will be blacked out and replaced by the patient's REDCap Record ID. The medication list and the flyer/referral form will be kept in a locked file cabinet in the health center.

### **3.) Behavioral Observation:**

While the patients are entering their medication information, the PI will be observing and recording on a checklist developed by the PI for this purpose the following: a) if the patient had difficulty visualizing the app; b) if they had difficulty with dexterity while using the app, and c) how many times the patient's input of medications needed to be corrected when entering their medications. The length of time from starting to download the app to completing set-up and

reviewing the app will also be recorded. The observation will occur once and will be recorded on a checklist by the PI while the patient is setting up the app with the help of the PI.

#### **D) RANDOMIZATION**

Once patients complete the baseline survey, patients will be randomized within each site to help reduce the likelihood of site bias. Patients will be randomized to either a wait list control group or the app intervention group. Randomization will be done by the PI automatically through REDCap. Intervention group patients will use the medication adherence app for 1-month and wait-list control group patients will receive a printed out copy of their medication list and have the name, dose, frequency and indication for their medications reviewed verbally with them by the PI. Both the intervention and wait-list control group will be contacted within the first week of enrolling in the study to see if they have any questions regarding the app or their medications in the case of the wait-list control. The follow-up measures will be completed by study patients in both the intervention and the wait-list control groups. At study completion, those randomized to the wait-list control group will be offered assistance by the PI to set up and use the app.

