## Study Protocol:

**A) RECRUITMENT :** The principal investigator (PI) will use the following recruitment strategies: in-person recruitment and clinician referral through use of the study flyer/referral form.

**In-person recruitment:** The PI will be present at the health center(s) on multiple days/week when health care providers (HCPs) and clinic staff see patients. The PI will work closely with HCPs and clinic staff to identify eligible patients and to how/when best approach eligible patients to introduce them to the study, anticipating it might be at the end of the visit in the exam room. The HCPs and clinic staff will introduce the PI to potentially eligible patients to introduce the study prior to the PI approaching the patient. Once the patient expresses interest in learning more about the study or indicates they would like to participate, the PI will follow the procedures as outlined in the study procedure section below.

**Eligibility:** 1) adults aged 18 years and older 2) speak and understand English 3) personally own and use an Android or iOS smartphone which is capable of downloading the Medisafe app and 4) take at least 1 medication for a chronic illness based on their computerized medical record at the health center.

**Clinician referral:** Study flyer/referral forms will be available in the patient exam rooms and/or in the medicine department's clinician office as determined/approved by clinic staff. Once a clinician identifies a potentially eligible patient, they or the patient may complete the study flyer/referral form. If the PI is present at the clinic, the form can be given directly to the PI. If the PI is not available, they will place it in a locked and secured collection box labeled "Smartphone App Study" only accessible by the PI. The box will be located in the general medicine department's clinician office or the appropriate exam rooms or as otherwise deemed necessary by clinic staff. The box will be checked, and forms collected at least once a week by the PI. Any patients who fill out a form will be contacted via their preferred method i.e., phone call, email or text message (see scripts for a phone call, email or text message) within one week by the PI.

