#### **E) INTERVENTION**

**1. Intervention Group:** The PI will assist the patient to download and set up the free Medisafe app on their smartphone at the clinic. The PI will use a unique URL, which can be texted or emailed to the patient, to facilitate the patient download of the HIPAA compliant app on their mobile smartphone. The PI will educate patients on how to use the app using educational materials developed for the study by the PI. The PI will also show patients the App “Help & Support” page, which answers commonly asked questions. This will be referred to as a “tutorial session.” Fidelity will be enhanced through the use of a “Checklist for App Set-Up” developed by the PI for the study to guide the App set-up process. The checklist with the patient record ID will be stored with the other study documents.

The following steps will be taken by the PI in this tutorial session:

- 1) Guide the patient with downloading the app to their phone.
- 2) Once the download is completed, the medication list, extracted from the chart, can be entered.
  - o Show patients how to enter the medication name, dosage, medication appearance (color and format of pill), frequency (every day, every other day, specific days of the week, etc.), the time the medication is regularly taken, and the number of pills left for the refill reminder (if the patient wants that option).
  - o If patients are having difficulty entering their medications, demonstrate the process by entering one of their prescribed medications. This will ensure the patient understands how to enter medications in the app.
  - o After the scheduled medications are added, show the patients how to access their list of medications in the app and how to edit a medication that was already in their list, e.g., change the medication dosage.

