## F. DATA ANALYSIS

IBM SPSS Statistics will be used for the quantitative summarization of the effects of the use of the app on the change in self-efficacy (SEAMS) and medication adherence (ARMS) from baseline to 1-month. Descriptive statistics will summarize sample characteristics and study measures. Raw change values from T1 to T2 in the adherence (ARMS), self-efficacy (SEAMS), medication social support, and medication knowledge scores will be calculated. Tests on the effects of the Medisafe app on those outcome measures will be conducted using multiple linear regression models. Given measurement error inherent in self-report measures, a reliable change index (RCI) criterium will be generated for each self-report measure. Each patient's raw change value will be evaluated against that criterium to determine whether the change was reliable or not and the direction of that change.

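### Patients are randomised within site, but the regression models do not name site; if several sites differ in mean change, leaving it out costs some power, usually little

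*Combined protocol and SAP*

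**What the plan says.** Section D makes site the only stated randomisation stratum: "patients will be randomized within each site to help reduce the likelihood of site bias". It describes two arms ("Patients will be randomized to either a wait list control group or the app intervention group") and the mechanism ("Randomization will be done by the PI automatically through REDCap"), but gives no allocation ratio and no blocking scheme.

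The number of sites is open. Section A has "The PI will be present at the health center(s) on multiple days/week", while the chart extraction part of Section C uses the singular: "The medication list and the flyer/referral form will be kept in a locked file cabinet in the health center".

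Section F sets the outcomes, "Raw change values from T1 to T2 in the adherence (ARMS), self-efficacy (SEAMS), medication social support, and medication knowledge scores will be calculated", and the test, "Tests on the effects of the Medisafe app on those outcome measures will be conducted using multiple linear regression models". It lists no covariates, so neither site nor the baseline score is named.

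**The concern.** The design treats site as something that may affect outcome, yet the written analysis does not say whether it will use it. If the stratum predicts change and is left out, between-site variation is counted as error. There are two cases.

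- **Arms balanced within site:** the estimate already benefits from the stratification, but the model does not know it. The reported standard error is too large and the test is conservative.
- **Allocation not blocked:** the reported standard error is valid, but the estimate is less precise than it could be.

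In both cases a real effect of the app is somewhat more likely to be missed. A second, smaller stake is that Section F leaves the covariate list open for four outcomes until the data are seen. Naming the stratum settles one part of that list, though only one.

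**Working it through.** The plan states no sample size, power, alpha or SD, so it has no figure to reproduce. The check shows a range instead.

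**Inputs.** From the documents: two arms, randomisation within site, outcome equal to change from T1 to T2. Assumed: two-sided 5% test, 80% power with site in the model, the same 1:1 ratio at each site, two equal sites unless stated. The site share f of the variance in change left unexplained by the other model terms is assumed to be 1% to 20%.

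**Formulas.**
- Gap between two equal sites, in within-site SD: 2·√(f/(1−f)).
- Standard error inflation when site is omitted: k = 1/√(1−f).
- Balanced: type I error = 2·(1−Φ(1.96k)); power = Φ(2.80−1.96k).
- Unblocked: type I error stays at 5%; power = Φ(2.80/k−1.96).

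Here 2.80 is 1.96 + 0.84, carried unrounded. Example at f = 5%: k = 1/√0.95 = 1.026 and 1.96k = 2.011. Type I error is 4.4%. Power is Φ(0.791) = 78.5% if balanced and Φ(0.771) = 78.0% if unblocked.

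| f | Gap (SD) | Type I, balanced | Power, balanced | Power, unblocked |
|---|---|---|---|---|
| 1% | 0.20 | 4.9% | 79.7% | 79.6% |
| 2% | 0.29 | 4.8% | 79.4% | 79.2% |
| 5% | 0.46 | 4.4% | 78.5% | 78.0% |
| 10% | 0.67 | 3.9% | 76.9% | 75.7% |
| 20% | 1.00 | 2.8% | 72.9% | 70.7% |

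These powers are for the model without site, against 80%. They do not charge the site term for its own cost.

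**Net comparison by simulation** (assumed: N = 100, two equal sites, a baseline covariate with coefficient −0.5 in both models, 20,000 replicates per cell). Power without and with site:

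| f | Blocks of 4: without / with | Net gain (points) | Unblocked: without / with | Net gain (points) |
|---|---|---|---|---|
| 1% | 79.31 / 79.52 | 0.2 | 78.85 / 78.77 | −0.1 |
| 2% | 79.25 / 79.90 | 0.7 | 78.68 / 79.03 | 0.4 |
| 5% | 78.16 / 79.79 | 1.6 | 77.86 / 79.36 | 1.5 |
| 10% | 76.94 / 80.11 | 3.2 | 74.90 / 79.07 | 4.2 |
| 20% | 72.92 / 80.11 | 7.2 | 70.26 / 79.06 | 8.8 |

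With site omitted, simulated type I error ran from 4.9% down to 2.9% with blocks, and between 4.9% and 5.2% without. The mean estimate under no effect was within 0.004 SD of zero in every cell.

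**Small unblocked trial** (assumed N = 40, 40,000 replicates per cell). Power without and with site:
- Two sites: f = 0, 77.8 and 76.5%; 1%, 77.5 and 76.9%; 2%, 77.1 and 76.9%; 3%, 76.5 and 76.5%; 5%, 75.8 and 76.8%. Break-even is near f = 3%.
- Four sites: f = 0, 77.7 and 74.0%; 2%, 77.2 and 74.3%; 5%, 75.7 and 74.2%. The site term loses 3.7, 2.9 and 1.5 points.

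With blocking and f = 0 the term cost nothing detectable at N = 100 (80.12 and 80.10%) or N = 40 (79.93 and 79.90%).

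**The case against.** The strongest reply is that little is at stake and that the remedy can cost more than it saves.

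- **Conditions.** A loss requires several sites, a difference between them in mean change, and an analyst who leaves site out. Multiple regression implies some term besides arm, and the stratum is an obvious candidate. This stands in part: what is shown is a term not named, not a term excluded. A reader might infer that the plan rules site out; it does not.
- **Small f.** Taking change from baseline removes stable site differences in level, and one investigator delivers much of the study ("The PI will assist the patient to download and set up the free Medisafe app on their smartphone at the clinic"). Low values of f are therefore the more plausible ones. This stands. The 10% and 20% rows need sites 0.67 and 1.00 SD apart in one-month change, and nothing in the documents suggests that.
- **Power lost by the fix.** If allocation is unblocked and the trial is small, a site term can lower power. This stands too, so the size must be stated net and the fix must allow for small sites.

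A reader might also infer that omitting site biases the estimate or produces false claims of benefit. The documents do not support that. With a common allocation ratio there is no bias as randomised, and type I error is at or below the nominal level. Bias would need allocation ratios that differ by site, or follow-up completion that differs by arm and site. The documents describe neither, although the follow-up procedures do anticipate late or missing surveys.

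**Conclusion.** The point holds as a minor one. The only stated stratum is not named in the analysis. If several sites enrol at one ratio and differ in mean change, omitting site gives a conservative test under balanced allocation, or a less precise estimate under unblocked allocation.

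With two equal sites and balanced allocation, the net loss from 80% power is under 1 point for f up to 2%, about 1.5 points at 5% and about 7 points at 20%. With unblocked allocation at N = 100 and two sites, the net gain from naming site is about zero at f = 1% and 0.4 points at 2%. At N = 40 it turns negative below about f = 3% with two sites, and about 2 to 4 points are lost with four sites for f up to 5%.

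All of this rests on assumed N, number of sites, ratio, blocking and f, because the documents give none of them. With one site the point disappears. A claim of a substantial power loss in this trial would go beyond the documents.

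**What to change.** Add to Section F: *The regression models include site (the randomisation stratum) as a fixed effect alongside study arm. Sites too small to support their own term are pooled by a rule fixed before the data are analysed by arm; if only one site enrols, the term is omitted.*

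The cost is that text and one degree of freedom per extra site. If allocation is not blocked, there is also a small loss of precision from chance imbalance between site and arm, which matters mainly in a small trial with several sites. Site must already be known in order to randomise within it, so no new data are needed. The change does not settle the rest of the covariate list.

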#### **E) INTERVENTION**

**1. Intervention Group:** The PI will assist the patient to download and set up the free Medisafe app on their smartphone at the clinic. The PI will use a unique URL, which can be texted or emailed to the patient, to facilitate the patient download of the HIPAA compliant app on their mobile smartphone. The PI will educate patients on how to use the app using educational materials developed for the study by the PI. The PI will also show patients the App “Help & Support” page, which answers commonly asked questions. This will be referred to as a “tutorial session.” Fidelity will be enhanced through the use of a “Checklist for App Set-Up” developed by the PI for the study to guide the App set-up process. The checklist with the patient record ID will be stored with the other study documents.

The following steps will be taken by the PI in this tutorial session:

- 1) Guide the patient with downloading the app to their phone.
- 2) Once the download is completed, the medication list, extracted from the chart, can be entered.
  - o Show patients how to enter the medication name, dosage, medication appearance (color and format of pill), frequency (every day, every other day, specific days of the week, etc.), the time the medication is regularly taken, and the number of pills left for the refill reminder (if the patient wants that option).
  - o If patients are having difficulty entering their medications, demonstrate the process by entering one of their prescribed medications. This will ensure the patient understands how to enter medications in the app.
  - o After the scheduled medications are added, show the patients how to access their list of medications in the app and how to edit a medication that was already in their list, e.g., change the medication dosage.

## Protocol for Dissertation Study

[name]

- In addition, for some of the medications already in the app's database, show the patient how to access information about the specific medication, including written information and a video about what the medication is for, what it may interact with, side effects etc.

3) Patients can choose what language they would like to use when using the App by toggling to the desired language.

4) Show the patient how to indicate that the medication was taken, skipped or rescheduled when they receive a reminder alarm to take their medication.

5) Introduce patients to additional app features including:

- a) Reports: how to check their weekly adherence report in which their adherence was calculated based on the number of times they clicked that the medications were taken.
- b) Medfriend: how to invite a family member or friend to be a Medfriend in the app. This process entails the patient adding the family members/friend's contact information in the form of a cell phone number and email and inviting them to download the app and obtain access to the patient's medication list and then they will receive an alert if the patient misses a scheduled medication dose.
- c) Under settings, how to set Medtones, snooze time, receive a morning reminder to take their medications with them and change the home screen style.
- d) How to access the help and support section.

[figure not shown]
The patient will be given the PI's contact information in case of any questions or concerns. The PI will follow up with the patient through text, email or phone call (whichever the patient prefers). This preference will be noted on the flyer/referral form as well as in an instrument entitled Subject Information in REDCap.

**2. Wait-list Control Group:** The wait-list control group patients will receive a printed out copy of their medication list and have the name, dose, frequency and indication for their medications and reviewed by the PI. They will be contacted within the first week of enrolling in the study to see if they have any questions regarding their medications. The follow-up measures will be completed by study patients in both the intervention and the wait-list control groups and feedback on the usefulness of the printed-out medication list and ways they used it to facilitate medication management. At study completion, The PI would make available the use of the app and will assist patients in setting up the app, as described above.

[figure not shown]
Screenshots of Android Screens:

# Protocol for Dissertation Study

[figure not shown]
[name]

[figure not shown]
Adding med

[figure not shown]
Daily overview timeline

[figure not shown]
Med reminder

[figure not shown]
Take dialog

[figure not shown]
Drug interactions

Updates feed

Medfriend

[figure not shown]

Status report

[figure not shown]
## Screenshots of iOS Screens:

## Protocol for Dissertation Study

[figure not shown]
[name]

[figure not shown]
Daily overview

Med reminder

[figure not shown]
Drug interactions

Updates feed

Med cabinet

Status report

## F. DATA ANALYSIS

IBM SPSS Statistics will be used for the quantitative summarization of the effects of the use of the app on the change in self-efficacy (SEAMS) and medication adherence (ARMS) from baseline to 1-month. Descriptive statistics will summarize sample characteristics and study measures. Raw change values from T1 to T2 in the adherence (ARMS), self-efficacy (SEAMS), medication social support, and medication knowledge scores will be calculated. Tests on the effects of the Medisafe app on those outcome measures will be conducted using multiple linear regression models. Given measurement error inherent in self-report measures, a reliable change index (RCI) criterium will be generated for each self-report measure. Each patient's raw change value will be evaluated against that criterium to determine whether the change was reliable or not and the direction of that change.
